7.2.5. Secondary Efficacy Endpoints

1. CNS Progression-Free Survival (PFS)

PFS is defined as the time from first day of study treatment until date of progression. Progression will be stratified into CNS progression (radiologic or cytology or clinical). CNS radiologic progression will be assessed by MRI criteria, CNS cytologic progression will be determined pathologically, and neurologic progression will be determined as per section 6.1.2.7 and Table 8 respectively. PFS will be calculated using the Kaplan-Meier method.

2. Overall Survival

Overall survival will be defined as the date of study entry until date of death from any cause. Cause of death will be recorded.

3. Safety

The primary safety objective of this trial is to characterize the safety and tolerability of pembrolizumab in subjects with LMD. The primary safety analysis will be based on subjects who experienced toxicities as defined by CTCAE, Version 4.0 criteria (Appendix 2). The attribution to drug, time-of-onset, duration of the event, its resolution, and any concomitant

medications administered will be recorded. AEs will be analyzed including but not limited to all AEs, SAEs, fatal AEs, and laboratory changes. Furthermore, specific immune-related adverse events (irAEs) will be collected and designated as immune-related events of clinical interest (ECIs) as described in Section 6.2.3.2

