3.2 Secondary Objectives

- (1) To determine whether pembrolizumab administered in patients with LMD from solid tumors improves CNS progression-free survival (PFS) as defined in section 4.1.5.1
- (2) To determine whether pembrolizumab administered in patients with LMD from solid tumors improves overall survival (OS), as defined in section 4.1.5.1
- (3) To determine whether pembrolizumab administered in patients with LMD from solid tumors, is safe and tolerable, as defined in section 4.1.5.1.

Hypothesis: Pembrolizumab will improve CNS-PFS and OS in patients with solid tumors and LMD.

Hypothesis: Pembrolizumab will be safe and tolerable in patients with LMD from solid tumors.

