4.1.4.5 Rationale for Anti-PD-1 Therapy in Patients with Leptomeningeal Disease

The most common solid tumors to metastasize to the leptomeninges include: NSCLC (25.8%), breast cancer (17.7%), small cell lung cancer (16.9%) and melanoma (8.9%) ⁵⁹. The incidence of LMD by disease-specific tumor type in the era of MRI scans, is estimated at: 3.8-5% of NSCLC patients^{60,61}, 5% of breast cancer patients⁶², 2-3% of patients with metastatic melanoma⁶³, 2-10% of SCLC patients⁶⁴, and 0.03% of patients with genitourinary carcinomas⁶⁵. The incidence of LMD is also projected to be higher in patients with oncogene-addicted cancers such as NSCLCs that harbor an activating mutation in the epidermal growth factor receptor (EGFR), or a chromosomal rearrangement such as EML4-ALK, or in patients with breast cancer that harbors a HER-2 mutation. These patients appear to have a longer clinical course than those without oncogenic driver mutations, and a subset of these patients tend to develop CNS progression with LMD. The median survival for patients with LMD is estimated at 3-6 months in recently published studies 33,39,66. While this is relatively rare group of patients, there are no established treatment options for this group of patients. These patients thus constitute a critical mass with an empty therapeutic niche. This, coupled with compelling early signals of therapeutic efficacy for pembrolizumab in patients with BM as detailed above, and the fact that pembrolizumab is a generally well-tolerated therapy, makes the use of this agent in patients with LMD an exciting potential treatment option.

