4.1.5.1 Efficacy Endpoints

4.1.5.1.1 Primary Endpoint:

The primary efficacy endpoint is to evaluate CNS response with pembrolizumab in patients with LMD from solid tumors. CNS response will be defined either as radiologic response, cytologic response, or clinical response, whichever is easier to assess. Radiologic response will be defined as a reduction in size of a measurable lesion on a contrast-enhanced MRI scan of the brain. Cytologic response will be defined as a negative CSF cytology result in 2 consecutive samples, in patients who have initial positive cytology prior to treatment, or a clinical response, defined as an improvement in objective neurologic signs or symptoms attributable to LMD (Table 8). Response assessment is detailed in section 6.1.2.7.

4.1.5.1.2 Secondary Endpoints:

- **1. CNS Progression-free Survival:** A secondary endpoint of this study is to evaluate CNS-PFS, which will be defined as the time from study enrollment until CNS progression (radiologic, cytologic or clinical), or death, whichever occurs first. CNS progression will be classified as radiologic (determined by contrast-enhanced MRI scan), cytologic (determined by pathologic assessment of CSF cytology including cell count, differential, glucose) or clinical progression (defined as new objective neurologic signs or symptoms, attributable to LMD), as detailed in section 6.1.2.7.
- 2. **Overall Survival:** A secondary endpoint of this study is to evaluate OS, which will be defined as the time from study enrollment until death from any cause. Deaths from progressive disease will be stratified as related to CNS progression, related to systemic progression, or both.

8A

3. **Safety:** Safety will be evaluated according to the National Cancer Institute Common Terminology Criteria for Adverse Events (NCI CTCAE) version 4.0^{27} safety will be determined by the number of treatment-related toxicities of > grade 3 severity by CTCAE Version 4.0.

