6.1.2.7.2. Tumor Imaging During the Trial

The first on study imaging assessment should be performed anytime between cycle 2 and 3 of planned therapy, and the second set of imaging should be performed anytime between cycle 4 and 5. In patients who only receive the planned 4 doses of therapy, this is replaced with the end of treatment MRI and CT, which should be done within 2 weeks of the last dose of therapy. Subsequent tumor imaging should be performed Q9W (±7 days) or more frequently if clinically indicated until PD. Imaging should not be delayed for delays in cycle starts or extension of pembrolizumab cycle intervals.

To assess radiologic response in the CNS, there are no standard radiologic response criteria for LMD on CT or MRI. The RANO group has proposed criteria for measuring BM⁷⁷, but not for LMD. From an extensive review of published literature of clinical trials and assessments of LMD in the modern MRI era^{33,78}, we propose using a radiologic cut-off of 3mm for measurable disease in the neuro-axis by gadolinium-enhanced MRI imaging of the brain and total spine including T1- weighted, T2-weighted, fluid attenuated inversion recovery and post-gadolinium sequences.

To assess for response outside of the CNS, per RECIST 1.1, partial or complete response should be confirmed by a repeat tumor imaging assessment not less than 4 weeks from the date the response was first documented. The tumor imaging for confirmation of response may be performed at the earliest 4 weeks after the first indication of response, or at the next scheduled tumor imaging (i.e. 9 weeks later), whichever is clinically indicated. Subjects will then return to regular scheduled imaging Q9W, starting with the next scheduled imaging time point. Subjects who obtain a confirmation imaging assessment do not need to undergo scheduled tumor imaging if it is < 4 weeks later and may wait until the next scheduled imaging time point.

Per irRECIST, if radiologic imaging identifies PD, tumor assessment should be repeated ≥ 4 weeks later in order to confirm PD with the option of continuing treatment while awaiting radiologic confirmation of progression. Subjects who obtain confirmation tumor imaging do not need to undergo scheduled tumor imaging if it is < 4 weeks later and may wait until the next scheduled imaging time point if clinically stable.

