Secondary endpoints will include CNS-PFS, OS and safety. Kaplan-Meier curves will be used to assess CNS-PFS and OS. Cause of death will be recorded. Safety will be assessed as detailed above, and monitored as per JHH SKCCC Data Safety and Monitoring Plan. Exploratory endpoints will include genomic testing of tumor cells and cell-free DNA in CSF and serum, and immunologic studies of immune cells in CSF and serum at pre-defined timepoints. These data will be presented descriptively. Genomic and immunologic correlates from available tissue in selected patients, will be presented descriptively. Means and standard deviations of all markers will be computed and 95% confidence intervals will be constructed. For serum markers, linear regression model (with proper transformation of the data) will be used to compare slopes in repeated measures between pre-defined time-points. Our institution sees 250 new patients per year with advanced lung cancer, 5% of which will have LMD (n=18 in 18 months), 200 new patients with breast cancer, 5% of which will have LMD (n=15 patients in 18 months), and selected patients with other solid tumors per year with LMD (n=10 per year), not including patients in follow-up. Taking into account that this may be a less fit patient population, we conservatively estimate that we will accrue 1 patient per month at our institution and 1 additional site that have agreed to participate in the study. Study duration will be approximately 24 months, allowing 18 months for accrual and 6 months for follow-up and data analysis.

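### Section 7.2.5 ends CNS-PFS at progression without naming death, while section 4.1.5.1.2, the definition cited by the secondary objective, counts death; the two also start the clock differently

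*Combined protocol and SAP*

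**What the plan says.** Two sections define the same secondary endpoint.

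- Section 4.1.5.1.2 (Secondary Endpoints) defines CNS-PFS as "the time from study enrollment until CNS progression (radiologic, cytologic or clinical), or death, whichever occurs first".
- Section 7.2.5 (Secondary Efficacy Endpoints), under the heading for CNS progression-free survival, says: "PFS is defined as the time from first day of study treatment until date of progression". It adds: "Progression will be stratified into CNS progression (radiologic or cytology or clinical". It names no death event and gives no censoring rule.

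Secondary objective 1 in section 3.2 asks whether treatment "improves CNS progression-free survival (PFS) as defined in section 4.1.5.1", so it points to the definition that includes death. For OS, section 7.2.5 says: "Overall survival will be defined as the date of study entry until date of death from any cause". On method, section 7.2.1 says: "Kaplan-Meier curves will be used to assess CNS-PFS and OS". Section 7.1 (Table 12) announces no formal inference.

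**The concern.** Progression-free survival normally counts death as a failure, and 4.1.5.1.2 does so. An analyst working from 7.2.5 alone could leave out a patient who dies without documented CNS progression, or censor that patient at death. The result would be a time-to-progression curve labelled as progression-free survival. The same data could then give two curves and two medians, and the choice between them would be open after the data are seen in an unblinded single-arm trial. The starting points (enrollment, first treatment day and, for OS, study entry) are not tied to one date either.

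**Working it through.** **1. The texts side by side**

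| | 4.1.5.1.2 | 7.2.5 |
|---|---|---|
| CNS-PFS starts at | study enrollment | first treatment day |
| CNS-PFS ends at | CNS progression or death | progression |
| Death named for CNS-PFS | yes | no |
| Censoring rule | none | none |
| OS starts at | study enrollment | study entry |

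**2. Does any text rank them?** Section 7.2.3 refers to Section 3.0 for the objectives, and objective 1 there refers to 4.1.5.1. That route leads to the definition with death. Against it, section 7.1 describes 7.2 as the comprehensive plan, and 7.2.5 writes out its own definition without referring back to 4.1.5.1.2. No sentence says which text governs.

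**3. The plan's own figures.** The documents state no figure for CNS-PFS. The sample size reproduces: 16 / (1 − 0.10) = 17.8, rounded up to 18. It does not depend on this endpoint.

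**4. Direction.** Assume a common origin, read progression in 7.2.5 as CNS progression (as its heading indicates), and censor deaths without CNS progression at the date of death. This censoring is an assumption, since 7.2.5 has no such rule. Both curves then have the same risk sets. At each event time with r patients at risk the Kaplan-Meier curve is multiplied by (1 − 1/r). The 7.2.5 curve skips that factor at every such death, so it can never fall below the other. Example with N = 16: if the first k events are all such deaths, the 4.1.5.1.2 curve reads 1 − k/16, and the 7.2.5 curve still reads 100%.

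- k = 1: 93.8%
- k = 2: 87.5%
- k = 4: 75.0%

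**5. Size, as an illustration.** Let f be the share of first events that are deaths without documented CNS progression. The documents do not give f.

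- Large sample, constant hazards: censoring these deaths multiplies the event hazard by (1 − f), so the median is multiplied by 1/(1 − f). For f = 2/16, 4/16 and 8/16 this is 1/0.875 = 1.14, 1/0.75 = 1.33 and 1/0.5 = 2.0.
- Simulation of single trials with N = 16, constant hazards, complete follow-up and exactly 2, 4 or 8 such deaths placed at random among the 16 first events (20,000 runs): the typical (median) within-trial ratio of the two Kaplan-Meier medians is about 1.13, 1.37 and 2.1. The two medians coincide in about 24%, 4% and 0% of trials.

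The within-trial ratio is the relevant one, because the question is what one data set would report under each definition.

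**The case against.** The strongest reply is that this is an omission, not a rival definition. Section 7.2.5 does not exclude death or tell anyone to censor it, its heading uses the term progression-free survival, and the route from 7.2.3 through objective 1 leads to 4.1.5.1. This largely stands as evidence of intent: death was very probably meant to count. It does not make the SAP text correct. Section 7.2.5 states a different end event and a different origin, and in the same section the OS definition names death explicitly.

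The reply also limits how far the point can be pushed. Three stronger readings are tempting.

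- **Early deaths.** Section 4.1.4.5 says: "The median survival for patients with LMD is estimated at 3-6 months in recently published studies". Section 6.1.2.7.2 says: "The first on study imaging assessment should be performed anytime between cycle 2 and 3 of planned therapy". With exponential survival, the proportion dead by day d at median m is 1 − 2^(−d/m). This runs from 7.7% (m = 6 months, d = 21) to 27.3% (m = 3 months, d = 42), or 1.2 to 4.4 of 16. A reader might infer that 1 to 4 patients would die without documented CNS progression. The documents do not support that. The calculation counts all early deaths under an assumed distribution, in a population less selected than the ECOG 0–1 patients enrolled here. Clinical CNS progression can also be recorded before any scan: Table 8 and 4.1.5.1.2 set no cycle limit, and Table 7 schedules an examination at every cycle. Only the text under Table 8 in section 6.1.2.7 attaches a two-cycle condition to new neurologic signs.
- **A large shift in origin.** A reader might take enrollment to mean consent, up to about 28 days before the first dose, because section 1.0 describes the accrual window by consent dates. Sections 4.2.8, 4.4 and 7.2.2 tie enrollment to registration or allocation, and section 4.3 starts treatment on the registration day or close to allocation. A gap near zero is the natural reading.
- **Guaranteed inflation.** The direction in step 4 needs a common origin. A later start under 7.2.5 shortens the times and works the other way.

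**Conclusion.** The inconsistency is real. Sections 7.2.5 and 4.1.5.1.2 differ in end event and origin, and no text settles which applies. Taken literally, 7.2.5 leaves deaths without documented CNS progression out of a progression-free survival endpoint. The upward direction holds only under a common origin, with progression read as CNS progression and censoring at death. The size is unknown; the ratios of about 1.13, 1.37 and 2.1 are illustrations that rest on an assumed 2, 4 or 8 such deaths, constant hazards and complete follow-up.

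A reader might infer that the plan deliberately excludes death. The citation in objective 1 speaks against that. A reader might also take the lack of a rule for patients who start new anti-cancer therapy as part of this contradiction. It is a separate matter of detail, and the two definitions can be reconciled without it.

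The endpoint is descriptive, and the primary endpoint and N = 18 are untouched. Because the analysis text is wrong as written and easily corrected, this is a should-fix at the low end.

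**What to change.** Amend 7.2.5 so that the CNS-PFS event is the earlier of CNS progression or death from any cause, in line with 4.1.5.1.2, with patients alive without CNS progression censored at their last CNS assessment. In both 4.1.5.1.2 and 7.2.5, state one time origin for CNS-PFS and OS. First dose matches the analysis population in Table 12 (eligible patients with at least one dose); registration should be nearly the same date.

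The cost is wording in two sections, settled before the analysis. Survival status and cause of death are already collected, so no new data are needed, and the sample size and primary endpoint stay as they are. The downside is that the reported median CNS-PFS may be shorter than under the present 7.2.5 wording.

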8. LABELING, PACKAGING, STORAGE AND RETURN OF CLINICAL SUPPLIES

8.1. Investigational Product

The investigator shall take responsibility for and shall take all steps to maintain appropriate records and ensure appropriate supply, storage, handling, distribution and usage of investigational product in accordance with the protocol and any applicable laws and regulations.

Clinical Supplies will be provided by Merck as summarized in Table 13.

Table 13. Product Descriptions

Product Name & Potency	Dosage Form
Pembrolizumab 50 mg	Lyophilized Powder for Injection
Pembrolizumab 100 mg/ 4mL	Solution for Injection

8.2. Packaging and Labeling Information

Clinical supplies will be affixed with a clinical label in accordance with regulatory requirements.

8.3. Clinical Supplies Disclosure

This trial is open-label; therefore, the subject, the trial site personnel, the Sponsor and/or designee are not blinded to treatment. Drug identity (name, strength) is included in the label text; random code/disclosure envelopes or lists are not provided.

8.4. Storage and Handling Requirements

Clinical supplies must be stored in a secure, limited-access location under the storage conditions specified on the label.

Receipt and dispensing of trial medication must be recorded by an authorized person at the trial site.

Clinical supplies may not be used for any purpose other than that stated in the protocol.

8.5. Returns and Reconciliation

The investigator is responsible for keeping accurate records of the clinical supplies received from Merck or designee, the amount dispensed to and returned by the subjects and the amount remaining at the conclusion of the trial.

Upon completion or termination of the study, all unused and/or partially used investigational product will be destroyed at the site per institutional policy. It is the Investigator's responsibility to arrange for disposal of all empty containers, provided that procedures for proper disposal have been established according to applicable federal, state, local and institutional guidelines and procedures, and provided that appropriate records of disposal are kept.

9. ADMINISTRATIVE AND REGULATORY DETAILS

9.1. Confidentiality

9.1.1 Confidentiality of Data

The investigator affirms to the Sponsor that information furnished to the investigator by the Sponsor will be maintained in confidence, and such information will be divulged to the institutional review board, ethics review committee (IRB/ERC) or similar or expert committee; affiliated institution and employees, only under an appropriate understanding of confidentiality with such board or committee, affiliated institution and employees. Data generated by this trial will be considered confidential by the investigator, except to the extent that it is included in a publication as provided in the Publications section of this protocol.

9.1.2. Confidentiality of Subject Records

The investigator agrees that the Sponsor (or Sponsor representative), IRB/ERC, or regulatory authority representatives may consult and/or copy trial documents in order to verify worksheet/case report form data. By signing the consent form, the subject agrees to this process. If trial documents will be photocopied during the process of verifying worksheet/case report form information, the subject will be identified by unique code only; full names/initials will be masked prior to transmission to the Sponsor.

By signing this protocol, the investigator agrees to treat all subject data use d and disclosed in connection with this trial in accordance with all applicable privacy laws, rules and regulations.

9.1.3 Confidentiality of Investigator Information

The investigator recognizes that certain personal identifying information with respect to the investigator, and all co-investigators and trial site personnel, may be used and disclosed for trial management purposes, as part of a regulatory submissions, and as required by law. This information may include:

. name, address, telephone number and e-mail address; [SEP]

- . hospital or clinic address and telephone number; [SEP]
- . curriculum vitae or other summary of qualifications and credentials; and sep-
- . other professional documentation. [SEP]

Consistent with the purposes described above, this information may be transmitted to the Sponsor, and subsidiaries, affiliates and agents of the Sponsor, in your country and other countries, including countries that do not have laws protecting such information. Additionally, the investigator's name and business contact information may be included when reporting certain serious adverse events to regulatory authorities or to other investigators. By signing this protocol, the investigator expressly consents to these uses and disclosures.

If this is a multicenter trial, in order to facilitate contact between investigators, the Sponsor may share an investigator's name and contact information with other participating investigators upon request.

9.1.4 Confidentiality of IRB/IEC Information

The Sponsor is required to record the name and address of each IRB/IEC member that reviews and approves this trial. The Sponsor is also required to document that each IRB/IEC meets regulatory and ICH GCP requirements by requesting and maintaining records of the names and qualifications of the IRB/IEC members and to make these records available for regulatory agency review upon request by those agencies.

9.2. Compliance with Financial Disclosure Requirements

Financial Disclosure requirements are outlined in the US Food and Drug Administration Regulations, Financial Disclosure by Clinical Investigators (21 CFR Part 54). It is the Sponsor's responsibility to determine, based on these regulations, whether a request for Financial Disclosure information is required. It is the investigator's/co-investigator's responsibility to comply with any such request.

The investigator/co-investigator(s) agree, if requested by the Sponsor in accordance with 21 CFR Part 54, to provide his/her financial interests in and/or arrangements with the Sponsor to allow for the submission of complete and accurate certification and disclosure statements. The investigator/co-investigator(s) further agree to provide this information on a Certification/Disclosure Form, commonly known as a financial disclosure form, provided by the Sponsor. The investigator/co-investigator(s) also consent to the transmission of this information to the Sponsor in the United States for these purposes. This may involve the transmission of information to countries that do not have laws protecting personal data.

